#### **11) Data and Specimen Banking\***

For STI measurement, a urine sample will be collected from the adolescent at each time point. Both the adolescent and the research assessor shall be present (at the same time) during the procedures outlined in this section. The procedures for the data to be stored or associated with each specimen are described below:

- (a) Both the adolescent and the research assessor shall keep the adolescent's urine specimen in view at all times before the specimen is sealed and labeled. If any of the specimen is transferred to another container, the research assessor shall ask the adolescent to observe the transfer and sealing of the container with a tamper-evident seal.
- (b) The research assessor shall place an identification label securely on each container. The label must contain the date, the adolescent's specimen number, and the adolescent's code number as the identifying information. The research assessor shall apply a tamper-evident seal on each container if it is separate from the label. The specimen bottle must be securely sealed to prevent undetected tampering.
- (c) The adolescent shall initial the identification label(s) on the specimen bottle(s) with his or her case ID in order to certify that the specimen was collected from him or her.
- (d) The specimen and chain-of-custody forms must be packaged for transfer to Quest laboratories. If the specimens are not immediately prepared for transfer, they must be appropriately safeguarded during temporary storage. The collected urine will be picked up by Quest laboratories a minimum of once per week.
- (e) While any part of the chain-of-custody procedures is being performed, the specimens and custody documents must be under the control of the involved research assessor. The assessor may not leave the collection site during the interval between presentation of the specimen by the adolescent and securing of the specimens with identifying labels bearing

the adolescent's specimen identification numbers and Case ID. If the involved assessor momentarily leaves his or her workstation, the sealed specimens must be secured or taken with him or her. If the assessor is leaving for an extended period of time, the specimens must be packaged for transfer to Quest laboratories and secured before the assessor leaves the collection site.

- (f) The specimen(s) sealed in a shipping container must be immediately transferred, appropriately safeguarded during temporary storage, or kept under the personal control of an authorized individual until transferred.
- (g) The research assessor shall ensure that a custody-and-control form is packaged with its associated urine specimen bottle.
- (h)

## 12) Data Management\*

### (a) Data Analysis Plan and Power Analysis

**H1a:** *eHealth Familias Unidas Primary Care will be effective, relative to Care as Usual, in reducing the frequency of (past 90-day) drug use in Hispanic adolescents over time.*

This hypothesis will be analyzed using Latent Growth Modeling (LGM). Growth models can be expressed in terms that are identical to models using random coefficients regression, mixed models or multi-level models, where the first level fits each response in time to an individual-level growth model. The second level represents the condition effect on the slope of drug use. LGM analyses will test for differences in trajectories of drug use over the 5 assessment time points among the 2 conditions. As recommended by Raudenbush and Bryk, we will use 2-level analysis to determine whether the mean trajectories of drug use for eHealth Familias Unidas Primary Care and prevention as usual differ significantly over time. Data analysis for this hypothesis and all others will be conducted using Mplus (v 7.2).

Power. Mplus Monte Carlo simulation with 10000 replications was used to calculate the power for this hypothesis using a latent growth curve model framework with one covariate (i.e., condition assignment) and missing data. With 5 time points (0, 6, 12, 24 and 36 months) and assuming a 5% attrition rate at each assessment (also assuming equal sample size across both conditions), with 228 cases in each condition at baseline (or 185 at the final assessment timepoint in each condition), we have 80% power to detect a regression coefficient equal to 0.09 (effect size = 0.3) in the regression of the slope growth factor on intervention condition. This is considered slightly over a small (0.2) effect size.

**H1b:** *eHealth Familias Unidas Primary Care will be effective, relative to prevention as usual, in reducing the frequency of (past 90-day) unprotected sex in Hispanic adolescents over time.*

The analytic plan and power analysis for this hypothesis are similar to that of H1a.

**H1c:** *eHealth Familias Unidas Primary Care will be effective, relative to prevention as usual, in reducing STI incidence (specifically, the incidence of gonorrhea and chlamydia).*

This hypothesis will be analyzed using a univariate logistic regression for the binary outcome, new diagnoses of STIs (Yes/No). STI incidence will be defined as a positive laboratory test result for a new chlamydia or gonorrhea infection at any of the four follow up assessment timepoints. In the analysis for this hypothesis, condition will predict STI diagnosis. The test of the hypothesis will be based on a Wald test comparing the intervention regression coefficient to its standard error. Additionally, the time of STI diagnosis will be included as a covariate in the logistic regression to test the robustness of the intervention's effect.

**Power.** According to CDC national statistics, the annual STI incidence rate is 3.16% for Hispanic adolescents aged 15 to 19. Thus, we expect the 3-year STI incidence rate in the control group to be approximately 9.2%. Using a one-sided Z test with pooled variance to test the difference between two independent proportions (assuming the same 5% attrition rate at each assessment timepoint), the study has over 80% power to detect a difference of 6.1% in STI incidence between the two conditions. This difference in proportions translates to an effect size of Cohen's  $h = 0.26$ , considered a small ( $h = 0.2$ ) to medium ( $h = 0.5$ ) effect size, according to Cohen (1988).

**H2a:** *Intervention effects on frequency of drug use will be partially mediated by improvements in family functioning over time.*

To test for mediation, we will use the "product of coefficients" test described by MacKinnon and colleagues, which is based on the distribution of the indirect effect of the intervention through the mediator (Cohen, 1988). This procedure tests whether the product of the coefficients from the intervention to the mediator (a) and from the mediator to the outcome (b) is significantly different from zero. Specifically, we will estimate paths between intervention and family functioning (a), and between family functioning and drug use (b). Because we have five time points, our first mediation analyses will fit bivariate growth curves for both family functioning and drug use and examine the role of the (latent) slope of family functioning on the slope of

drug use. The product of the two pathways  $(a) \times (b)$  is the indirect effect of eHealth Familias Unidas Primary Care to drug use through the family functioning trajectory. As noted above, we will be testing whether the product  $(a) \times (b)$  is statistically significantly different from zero, by comparing the observed value of  $(a) \times (b)$  to the empirical distribution calculated using the bias-corrected bootstrap. In addition to this long-term developmental mediation model, we will also test if the initial changes in family functioning from baseline to the 6 month follow-up mediate the effect of intervention on drug use trajectory. Our team has expertise in conducting mediational analyses in multilevel models.

Power. Mplus Monte Carlo simulation with 10000 replications was used to calculate the power for this hypothesis using a mediation model framework. With a final sample size of 370 (assuming 5% attrition rate at each assessment timepoint), we have 80% power to uncover a significant mediating effect when the regression coefficient of pathways 'a' is approximately -0.36 and 'b' is approximately -0.18 (i.e.,  $R^2$  effect size were 0.033 for the relationship between X and M (i.e., path 'a;') and M and Y (i.e., path 'b'), which is considered a small effect (Cohen, 1988).

***H2b: Intervention effects on frequency of unprotected sex will be partially mediated by improvements in family functioning over time.***

The analytic plan and power analysis for this hypothesis are similar to that of H1b.

***H2c: Intervention effects on STI incidence will be partially mediated by improvements in family functioning and decreases in unprotected sex over time.***

We will use MacKinnon's method described in H1b with the exception that the outcome for this hypothesis is binary. The Weighted Least Squares Means and Variance adjusted (WLSMV) estimator in Mplus will be used to estimate the indirect effect. With WLSMV, a continuous latent response variable ( $y^*$ ) underlying the observed dichotomous variable is used to test for the mediated or indirect effect.

Power. We aimed to identify the minimal detectable regression coefficient for the mediator based on Vittinghoff and colleagues' methodology. The results show that we have 80% power to detect a mediating effect if the logistic regression coefficient for the mediator is 0.63, which is equal to an OR of 1.88, corresponding to an effect size of  $d = 0.35$ . According to Cohen, this is considered a small ( $d = 0.2$ ) to medium ( $d = 0.5$ ) effect size.

(b) Secure Data and Quality Control

All adolescent and parent self-report measures will be administered electronically through a tablet.

Data will be uploaded weekly in a database housed on a server maintained and secured by the University of Miami Department of Public Health Sciences. The server is password protected as well as protected by a firewall. The Principal Investigator will have access to the data electronically on his password protected laptop. His designees (i.e. Project Coordinator and Statistician) will also have access to electronically stored data. Principal Investigator and his team are on the tenth floor of the Clinical Research Center at [name].

We will also collect identifying data (e.g. participant name and contact information). This data will be collected electronically and stored in secure University of Miami systems. We will use a record system in which all participant records are filed numerically by case number, with no identifying information attached to the outcome data. A master sheet, with individual names and their respective code numbers will be kept electronically and accessed only under the supervision of the Principal Investigator. No one other than the Principal Investigator, the Project Coordinator, and approved study staff will have access to records identifying subjects' names at any time. Only the Principal Investigator and the Project Coordinator (under the supervision of the Principal Investigator) will have access to both the participants' identifying information and their assessment data.

(c) Data and Specimen

If both the parent and adolescent have agreed to these tests, urine will be collected from adolescent participants to test for gonorrhea and chlamydia. The research assessor will be responsible for properly implementing urine collection procedures, storing and labeling (without identifiers) the collected urine. Urine will be collected from the adolescent in a completely private manner; at no moment will the assessor watch the adolescent collect the urine specimen. The urine will be analyzed by Quest Diagnostics. Detailed procedures are outlined in section 11) Data and Specimen Banking.

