First Efficacy Study of Familias Unidas in a School Setting. [name] and colleagues evaluated the efficacy of Familias Unidas in preventing adolescent drug use, cigarette use, alcohol use, and unprotected sexual behavior, relative to (1) an HIV preventive intervention and (2) a cardiovascular preventive intervention. Participants ( $n = 266$ , mean age = 13.4,  $SD = .68$ ) were assessed at baseline, randomized, and reassessed at 6, 12, 24, and 36 months post baseline. Familias Unidas was efficacious, relative to the cardiovascular intervention in reducing past 90-day illicit drug use ( $z = 2.02$ ,  $p < .05$ ), efficacious relative to both the HIV intervention ( $z = 3.25$ ,  $p < .002$ ) and the cardiovascular intervention ( $z = 2.66$ ,  $p < .008$ ) in reducing past 90-day cigarette use, and in reducing unprotected sexual behavior at last sexual intercourse ( $X^2(1) = 3.87$ ,  $p < .05$ ). The effects of Familias Unidas were partially mediated by improvements in family functioning. Finally, post-hoc analyses also showed that the incidence of (self-reported) STIs in Familias Unidas was significantly lower than for adolescents in either of the two control conditions (Fisher's Exact  $p$ -value = .05).

Second efficacy study of Familias Unidas in a School Setting. [name] and colleagues evaluated the efficacy of Familias Unidas in preventing adolescent substance use as well as unprotected sexual behavior, relative to prevention as usual in a sample of behavior problem youth. 213 participants (mean age =14.3,  $SD =0.7$ ) and their primary caregivers were enrolled. Participants were assessed at baseline, randomized, and reassessed at 6, 18, and 30 months post baseline. Analyses showed a significant difference in past 30-day substance use ( $b=0.53$ ,  $z =2.42$ ,  $p < .02$ ;  $d =0.25$ ) and in the frequency of condom use ( $b= -0.306$ ,  $z = -2.214$ ,  $p<.03$ ;  $d =0.30$ ) between Familias Unidas and prevention as usual.

Third efficacy study of Face-to-Face Familias Unidas in a School Setting. [name] and colleagues evaluated the efficacy of Familias Unidas in reducing past-90 day illicit drug use and unprotected sexual behavior, relative to prevention as usual, among adjudicated Hispanic youth. 212 (mean age = 14.6,  $SD = 1.36$ ) juveniles and their primary caregivers were assessed at baseline and reassessed at 6 and 12 months post baseline. The results showed that Familias Unidas was efficacious, relative to

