prevention as usual, in improving family functioning ( $b=.28$ ,  $p=0.02$ ), increasing past 90-day condom use ( $b=0.68$ ,  $OR = 1.97$ ,  $p=0.015$ ), and in reducing past 90-day illicit drug use ( $b=-0.72$ ,  $p=0.04$ ).

Face-to-Face Effectiveness Study of Familias Unidas in a School Setting. [name] and colleagues (under review) evaluated the effectiveness of face-to-face Familias Unidas in reducing the frequency of drug use, alcohol use, and unprotected sexual behavior, relative to prevention as usual, among 746 Hispanic youth (mean age = 13.9,  $SD = 0.67$ ) recruited from 18 middle schools. School counselors were trained to deliver Familias Unidas. Participants were assessed at baseline and reassessed at 6, 18 and 30 months post baseline. The results showed that there was, a significant intervention effect on drug use frequency ( $b = -0.201$ ,  $p < 0.001$ ,  $d = 0.265$ ). Among participants who reported being sexually active ( $n = 130$ ) in the 90 days prior to any of the assessments, the analyses showed significant differences between Familias Unidas and Prevention as Usual in past 90 day condom use frequency ( $b = 0.093$ ,  $p = .008$ ,  $d = 0.98$ ). At 6 months post-baseline, parents of youth randomized to Familias Unidas reported significantly higher levels of family functioning relative to parents of youth randomized to Prevention as Usual ( $b = 0.148$ ,  $p = 0.014$ ,  $d = 0.47$ )

Efficacy Study of eHealth Familias Unidas in School Settings. In an ongoing randomized trial, [name], [name] and colleagues are investigating the efficacy of an eHealth adaptation of Familias Unidas in reducing drug use and unprotected sex relative to prevention as usual among 256 Hispanic youth (CDC Grant # U01PS003316; [name], PI; [name], Mentor). eHealth Familias Unidas was developed utilizing the intervention manual from the face-to-face Familias Unidas intervention, and an independent rater determined that 91% of the components of face-to-face Familias Unidas were present in the eHealth adaptation. Details on eHealth Familias Unidas and its components are described under “eHealth Familias Unidas Primary Care.”

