The 6 month follow up has been completed for this study and preliminary results indicate that eHealth Familias Unidas in schools has high family engagement (mean number of sessions = 8.4 out of 12;  $SD = 4.6$ ) and is having a significant effect on parent-adolescent communication ( $b = -5.11$ ;  $p = .05$ ; see Figure below), the intervention’s mediator. Results on drug use and unsafe sexual behavior are in the expected direction and of similar effect size as in previous Familias Unidas trials (effect sizes = 0.79 and 0.40 for drug use and unsafe sex, respectively) at 6 month follow up. It is worth noting that in all of our intervention trials, changes in parent-adolescent communication were observed between the baseline and 6-month follow up assessment, and those changes in turn significantly impacted the distal outcomes, drug use and unsafe sex, at subsequent time points.

Pilot Study of eHealth Familias Unidas in Primary Care. [name] and colleagues evaluated the feasibility and acceptability of delivering eHealth Familias Unidas

Primary Care in a universal sample of Hispanic youth. Study staff recruited 48 Hispanic youth and their primary caregivers from four sites: a mobile clinic, an academic pediatric clinic, a public health clinic (Jackson Memorial Hospital), and a private practice clinic (Kidstown Pediatrics, LLC). The pilot study's aim was not to assess efficacy or effectiveness but rather to assess the: 1) feasibility of recruiting families from pediatric care clinics, 2) feasibility of having pediatric clinic personnel deliver eHealth Familias Unidas, and 3) acceptability of the intervention from both the participants' and clinic staff's perspective.

To recruit study participants, our study team interfaced with pediatric care staff. Clinic staff let the study team know when (date and time) Hispanic youth between the ages of 12 - 16 (the target age range for the proposed study) and their caregivers were scheduled. During those times, a recruiter/assessor was present to recruit, consent and screen the family. Parent-child dyads were eligible to participate if they self-identified as Hispanic, the youth was between the ages of 12 - 16, both youth and parent were willing to participate, the parent had Internet access, and the family did not have plans of moving from South Florida within the next year.

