- Frequency of (past 90-day) unprotected sex in Hispanic adolescents over time.
- STI incidence (specifically, the incidence of gonorrhea and chlamydia).

ii) Secondary:

- Improvements in family functioning over time (e.g. parent-adolescent communication, parental monitoring of peers).
- Frequency of unprotected sex will be partially mediated by improvements in family functioning over time.
- Reduction of STI incidence will be partially mediated by improvements in family functioning and decreases in unprotected sex over time.

(b) Safety endpoints

Not applicable.

10) **Procedures Involved**

(a) Study Design

This study tests the effectiveness of eHealth Familias Unidas Primary Care in preventing drug use, unprotected sexual behavior, and STIs in a universal sample of Hispanic youth, this study will use a randomized trial design with two levels of intervention (eHealth Familias Unidas Primary Care and prevention as usual) as the between subjects factor with five repeated measures assessments at baseline, 6, 12, 24, and 36 months post baseline as the within subject factor.

Once both primary care giver and adolescent have completed the consent/assent, they will complete the baseline assessment electronically. Once the baseline assessment is complete, they will be randomized to one of the two conditions: eHealth Familias Unidas Primary Care (experimental prevention as usual (control) Condition. Please see attached for consent/assent forms (in English and Spanish). All consent forms will be completed electronically. All confidential study participant information will be stored electronically in secure University of Miami systems.

i) eHealth Familias Unidas Primary Care

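### Does the unprotected-sex hypothesis (H1b) need its own model and power calculation rather than a reference to H1a?

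*Combined protocol and SAP*

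**What the plan says.** Section 9(a) lists the frequency of unprotected sex over the past 90 days among three primary endpoints. Section 12(a) gives H1b one sentence: "The analytic plan and power analysis for this hypothesis are similar to that of H1a".

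Under H1a the method is a two-level latent growth model over five visits, testing the effect of condition on the slope. Its power statement, for 228 per arm at baseline and 5% attrition at each assessment, is "we have 80% power to detect a regression coefficient equal to 0.09 (effect size = 0.3"). Neither hypothesis has a stated alpha or sidedness. H1b adds no expected share of sexually active youths, no outcome distribution and no explicit scoring rule for inactive youths.

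Three other places bear on this:
- Section 10(a) describes the aim as effectiveness "in preventing drug use, unprotected sexual behavior, and STIs in a universal sample of Hispanic youth".
- Section 4(b) reports earlier effects. The second efficacy study gives d = 0.30, described as a difference "and in the frequency of condom use". The eHealth school study gives preliminary "effect sizes = 0.79 and 0.40 for drug use and unsafe sex, respectively) at 6 month follow up". The school effectiveness trial gives d = 0.98 for condom use, introduced by "Among participants who reported being sexually active" and based on 130 of 746 youths.
- For H1c, Section 12(a) says "we expect the 3-year STI incidence rate in the control group to be approximately 9.2"%.

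**The concern.** Drug use and unprotected sex need not behave alike. In the school effectiveness trial 130/746 = 17.4% of youths were sexually active in any of the 90-day windows before an assessment. With a similar share here, more than four in five adolescents would score zero at every visit, and any effect among active youths would be diluted in the full sample. An 80% figure simulated for another outcome would then say little about H1b, and a null result on a primary hypothesis could not be told from an underpowered one.

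Two further points add to the unease. The school trial analysed condom use in active youths only. If the same were done here, the comparison would condition on behaviour after randomization. And H1c's 9.2% seems hard to square with 17.4% active.

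**Working it through.** **The plan's own figure.** Final numbers: 228 × 0.95⁴ = 185.7 per arm, matching the stated 185. The growth-model simulation cannot be rerun exactly, because time coding and residual variance are not given. As a rough check, a two-group comparison with 185 per arm, d = 0.3 and two-sided 0.05 (assumed) has noncentrality 0.3 × √(185/2) = 2.885 and power Φ(2.885 − 1.96) = 82%. The effect detectable with 80% power is 2.8016 × √(2/185) = 0.291. So 80% at 0.3 is plausible, and it is taken as given below.

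**Translating 0.3 to active youths.** Let p be the active share, with all others at zero, and d_a the effect in SD units among active youths. Let m be the mean-to-SD ratio of the slope among active controls (assumed 0 to 1). Assume no effect on becoming active. Then

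overall d = p·d_a / √(p + p(1−p)m²)

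power = Φ(2.8016 × d/0.3 − 1.96), the other tail being negligible.

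Example with p = 0.1743: at m = 0 the factor multiplying d_a is 0.417, so an overall 0.3 needs d_a = 0.3/0.417 = 0.72. At m = 1 the factor is 0.309 and d_a = 0.97.

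| Active share | Power, d_a = 0.30 | Power, d_a = 0.40 | Power, d_a = 0.98 | d_a needed for overall 0.3 |
|---|---|---|---|---|
| 17.4% | 14-22% | 21-35% | 81-97% | 0.72-0.97 |
| 35% | 25-38% | 40-60% | 99% or more | 0.51-0.65 |
| 50% | 37-51% | 58-75% | over 99% | 0.42-0.52 |

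The ratio m matters. At m = 2 and 17.4% active, power is about 8-9%, 12% and 45%, so the ranges are scenarios, not bounds.

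**Which column applies.** Only the 0.98 is reported among active youths. The descriptions of the 0.30 and 0.40 do not say whom they cover. Over all youths, 0.30 gives 80% and 0.40 gives Φ(2.8016 × 0.40/0.30 − 1.96) = 96%. The 0.30 and the 0.98 also concern condom use, not frequency of unprotected sex.

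**Is 17.4% right here?** That cohort had mean age 13.9 and 30 months of follow-up; this trial enrols ages 12-16 for 36 months. H1c's 9.2% follows from the cited annual rate: 1 − (1 − 0.0316)³ = 9.2%. Divided by the active share it implies 0.092/0.1743 = 53%, 0.092/0.35 = 26% or 0.092/0.50 = 18% of active youths infected. The comparison is loose: one figure counts 90-day windows, the other accumulates over three years, and the STI rate is for ages 15-19. It does suggest that the planners had a larger active share in mind.

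**Does the carried-over model fail on such data?** In simulated trials with zero-heavy counts, the ordinary model-based slope test had type I error of 3-5% at 17-50% active, with standard errors and power close to robust ones. In a further set of 4,000 simulated trials, a linear slope with cluster-robust errors gave 4.5%, 4.5%, 4.5% and 4.1% at 17.4%, 25%, 35% and 50% active. That set assumed a mean of 6 events per 90 days once active, lognormal SD 1 between youths and gamma dispersion 1; about 86% of youths were all-zero at 17.4% active.

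**The case for a change.** The strongest case for a change is that a primary hypothesis should not rest on a simulation done for another outcome. With 17.4% active, effects of 0.30 to 0.40 among active youths would have 14-35% power, and even at 50% active they stay below 80%. Stating the active share, the distribution and the scoring of zeros would cost only some text and one rerun simulation. It would also close off later choices about scoring and model.

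Part of this stands. H1b's power is not shown separately, and the low-power arithmetic is correct under its conditions. But those conditions are chosen, not documented: a low active share, modest effects confined to active youths, no effect on initiation, and m of 0-1. The programme aims at prevention, so delayed initiation could add to the effect. Nor does the formula test the plan's number; it assumes 80% at an overall 0.3 and re-expresses that on another scale.

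The worry about analytic freedom is limited. The reference to H1a brings in the growth model and the slope test. The endpoint is defined in the adolescents as a whole. The instrument in Section 10(c) records numbers of times, so a youth with no sex scores zero. The plan proposes no active-only analysis for this trial. Whether to use a count model instead is a fair trade-off.

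**Conclusion.** No change follows. The H1b text is thin, but followed as written it gives a workable analysis: the H1a growth model, in all adolescents, with zeros for those not active. In simulated zero-heavy data that test keeps its error rate at about 3-5%.

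The borrowed power statement is a detectable effect of 0.3, and the documents do not show it to be wrong. Depending on inputs they leave open, H1b's power at the effects reported earlier runs from about 14% (0.30 among active youths only, 17.4% active, m = 1) to about 97% (0.98 among active youths, 17.4% active, m = 0), with 80% or 96% if 0.30 or 0.40 covers all youths. These figures assume two-sided 0.05, the plan's 80% at 0.3, and no effect on initiation. Low power is possible but not established. Writing down the missing inputs would help a reader interpret a null result; it would not alter enrolment, the test or the estimate.

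One clerical slip lies nearby. The H2b text says "The analytic plan and power analysis for this hypothesis are similar to that of H1b", and H2c likewise points to H1b for the mediation method, which is in fact described under H2a. Both probably mean H2a, and an analyst would read them so.
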